**Study Number: 2010-0243**

**NCT01143389**

**Version 2, Sept 12, 2017**

### *Main Outcome Measure*

The main efficacy outcome is the change in maximum keratometry (assessed by corneal tomography) from baseline to the 6-month post-treatment examination. This will be assessed for the per-protocol population as well as the intent-to-treat (randomized) population. The last-observation-carried-forward method will be used to impute missing data for participants lost to follow-up in the intent-to-treat analysis.

### *Null and Research Hypotheses*

The null hypothesis is that the 2 riboflavin dosing frequencies do not produce equivalent results and the research hypothesis is that they do produce equivalent results. Equivalence will be assessed with a 2 one-sided test at the 0.05 significance level. A clinically relevant margin of equivalence is considered to be  $\pm 0.75$  D. Enrollment of 510 patients will provide 80% power to determine whether the 2 treatment arms are equivalent within this margin of equivalence, assuming a mean change in maximum keratometry of -1.0 D in each group, a standard deviation of 2.7, and 10% loss to follow up during the 6-month follow up period.

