6 Months	196	53.9003	52.6523	-1.24801	-1.83121	0.001013	0.002256
1 Year	136	53.7790	52.3346	-1.44449	-2.35446	0.000025	0.000039
2 Years	60	54.0197	52.4340	-1.58567	-2.52731	0.001214	0.001250
4 Years	30	53.4627	50.7030	-2.75967	-4.58245	0.000396	0.000342
5 Years	13	52.2777	50.0723	-2.20538	-3.78418	0.020667	0.019656
6 Years	5	50.6400	48.1740	-2.46600	-4.81223	0.064549	0.067719
7 Years	4	52.3825	49.4500	-2.93250	-5.48322	0.057697	0.056259
8 Years	1	47.3400	47.1400	-0.20000	-0.42248	.	.

Kohlhaas presented results for 127 of these eyes at the 2005 Congress of the German-Language Society for Intrakularlinsen Implantation and Refractive Surgery with a follow-up of up to 60 months. Progression of keratoconus was stopped in all the eyes, and 81.7% of them showed a mean decrease of 2.87 D in Kmax. No opacification of the lens or change in endothelial cell density was seen in any patient. Long term follow-up results in a subset of 60 eyes in the Dresden Clinical Study that underwent cross-linking 3-5 years ago confirm the lasting effects of cross-linking in that there has been no progression of keratoconus in any of the eyes and 51.2% (31/60) of the eyes have a slight reversal and flattening of the Kmax. Kohlhaas et al. also reported a patient who developed bilateral keratectasia at 4 weeks after LASIK and underwent UVA/riboflavin cross-linking 6 months later. In this case, corneal topography remained stable for 18 months after cross-linking.

Sixty-six eyes in 49 patients have been enrolled in an Australian randomized study of observation-only control versus cross-linking in eyes with progressive keratoconus.¹ Maximum K-readings taken before and at 6 and 12 months after cross-linking showed a mean decrease of -0.92 diopters and -1.45 diopters in the treatment group (P=0.002).¹ In contrast, the untreated control eyes show a statistically significant increase of 0.60 D and 1.28 D in K-readings at 6 and 12 months after randomization.¹ The treatment group also showed an improvement in BSCVA, while BSCVA in the control group worsened.

Similar to the Dresden experience, these data lead to the conclusion that corneal cross-linking halts, and even reverses, the progression of keratoconus.

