- Optical coherence tomography (OCT)
- Corneal topography
- Intraocular pressure (by Goldmann applanation tonometry)
- Slit lamp examination of the cornea, anterior chamber and lens
- Dilated fundus examination

Randomization

Subjects will be classified as having keratoconus, post-refractive ectasia, or pellucid marginal degeneration. In addition those with keratoconus will be classified as mild (flat keratometry reading $< 51.00D$), moderate (flat keratometry reading of 51.25 to $56D$ or astigmatism $\geq 8D$), or severe (flat keratometry reading $>56D$). Block randomization will be employed to ensure representation of each classification in both treatment groups. If a subject has both eyes affected by the condition, the first eye treated will be randomized and the fellow eye will not. Fellow eyes will not be included in the efficacy analysis and will be dosed at 5 minute intervals during irradiation.

Subjects who elect to be treated will undergo the following procedure:

Treatment:

Subjects will be prepared for treatment in accordance with the instructions for use in the UV-X™ Illumination System Operator's Manual, including the administration of the riboflavin and preoperative medications (e.g. topical anesthetics).

Prior to the treatment, the presence of an informed consent for it will be confirmed. Patients will receive a therapeutic contact lens after the treatment is complete. An operative report or chart note will be placed in the subject's medical records documenting the procedures used for each patient. Selected treatment information, including the riboflavin administration, irradiance settings, and duration of irradiation exposure will be documented.

The subject will lie on a surgical table or chair with the head supported in a headrest. The bed will be adjusted so the subject can lie flat or recline comfortably for the duration of the procedure without moving. The skin around the eye and the conjunctival surfaces will receive a surgical cleansing. Topical anesthesia will be applied and a lid speculum will be placed between the lids of the eye to be treated. The surgeon will remove the epithelium from a circular area approximately 6 mm in diameter centered on the maximum of the posterior float on the corneal tomography assessment performed at the screening visit. Additional local anesthetics will be applied as needed.

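### The primary equivalence test names no covariates; adjusting for baseline Kmax and the randomisation classes would gain precision at almost no cost

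*SAP*

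**What the plan says.** SAP, Null and Research Hypotheses, gives the primary test in one sentence: "Equivalence will be assessed with a 2 one-sided test at the 0.05 significance level". The margin is ±0.75 D. The sample size statement is "Enrollment of 510 patients will provide 80% power", on the assumption of the same mean change of -1.0 D in both arms and "a standard deviation of 2.7, and 10% loss to follow up during the 6-month follow up period". No model or covariate is named there, in SAP, Main Outcome Measure, or in Protocol, Data Analysis. The main outcome is to be assessed in the per-protocol and the intent-to-treat populations; for the latter, "The last-observation-carried-forward method will be used to impute missing data".

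Protocol, Randomization, sorts subjects by diagnosis (keratoconus, post-refractive ectasia, pellucid marginal degeneration) and divides keratoconus into mild, moderate and severe by flat keratometry and astigmatism. It then states: "Block randomization will be employed to ensure representation of each classification in both treatment groups". The procedure schedule has corneal tomography at screening, so baseline Kmax is available for every study eye. It is also needed to compute the outcome.

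**The concern.** The allocation is balanced on five classes that the analysis then ignores, and the baseline value of the outcome is not used beyond being subtracted. If either is related to the change in Kmax, the unadjusted comparison has a wider confidence interval than the same data allow. In an equivalence trial the cost is inconclusiveness: the 90% CI may cross ±0.75 D although the two regimens do not differ. It does not make a false claim of equivalence more likely.

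**Working it through.** **Step 1. Reproduce the plan's power.** Inputs from SAP, Null and Research Hypotheses: margin 0.75 D, SD 2.7 D, true difference 0, 0.05 for each one-sided test, 510 enrolled, 10% loss. Completers: 510 × 0.9 = 459, or 229.5 per arm if allocation is 1:1 (the ratio is not stated).

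- SE = 2.7 × √(2/229.5) = 0.252 D.
- Normal approximation: 2Φ(0.75/0.252 − 1.645) − 1 = 81.7%.
- Exact t version, integrating over the sample variance: **81.5%**.

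The stated 80% is reproduced, slightly on the safe side.

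**Step 2. Does baseline Kmax look prognostic?** The K-max table in Protocol, Clinical Experience, gives the mean change in dioptres and the mean percent change. The single eye at 8 years (−0.20/47.34 = −0.42248%) confirms that percent means change divided by baseline. If change were unrelated to baseline, the mean percent change would be expected to be at least as negative as mean change/mean baseline, because E[1/b] ≥ 1/E[b] and the mean change is negative. The table shows the reverse in all seven rows with more than one eye:

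| Row | N | Mean change / mean baseline | Mean percent change |
|---|---|---|---|
| 6 months | 196 | −2.32% | −1.83% |
| 1 year | 136 | −2.69% | −2.35% |
| 2 years | 60 | −2.94% | −2.53% |
| 4 years | 30 | −5.16% | −4.58% |
| 5 years | 13 | −4.22% | −3.78% |
| 6 years | 5 | −4.87% | −4.81% |
| 7 years | 4 | −5.60% | −5.48% |

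The direction is that eyes steeper at baseline flattened more.

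**Step 3. Rough size of the relation.** With d the mean change, b the mean baseline, m the mean of change/baseline and s the baseline SD, a second-order expansion gives cov = b²(d/b − m + d·s²/b³). Two assumptions are needed: a value of s (not reported), and that the table's p-values are two-sided paired t tests (the test is not named). The second gives an SD of change of |d|√N/t = 5.24 D at 6 months. For s = 8 D at 6 months:

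- cov = 53.9003² × (−0.02315 + 0.01831 − 0.00051) = −15.6 D².
- r = −15.6/(8 × 5.24) = −0.37, so R² = 0.14.

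For s from 6 to 10 D, R² runs from 0.23 down to 0.10 at 6 months and from 0.21 down to 0.10 at 1 year. R² values of 0.1 and 0.2 are therefore used below as illustrations, not as estimates for this trial.

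**Step 4. Power with adjustment.** Residual SD = SD × √(1 − R²). Residual df = 459 − 7 = 452 (intercept, treatment, baseline Kmax, four class terms). At SD 2.7 D the residual SD is 2.56 D or 2.41 D.

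| SD of change | Unadjusted | R² = 0.1 | R² = 0.2 |
|---|---|---|---|
| 2.7 D | 81.5% | 86.3% | 90.6% |
| 3.0 D | 69.7% | 76.0% | 82.1% |
| 3.5 D | 48.3% | 55.9% | 64.1% |

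The SD up to which 80% power is kept rises from 2.74 D to 2.89 D or 3.06 D. In sample-size terms, 459 completers would do the work of 459/0.9 = 510 or 459/0.8 = 574.

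**Step 5. Cost if nothing is explained.** With R² = 0 the only loss is five degrees of freedom. Power at SD 2.7 D is 81.5% either way to one decimal; in a simulation with blocked allocation it was 81.6% adjusted against 81.7% unadjusted.

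**The case against.** The strongest reply is that nothing here is an error. Randomisation makes the unadjusted test valid, the sample size statement gives its assumptions, and its arithmetic is right. That stands. A reader might infer that ignoring the blocking classes inflates the type I error. It does not: prognostic blocking that is left out of the analysis makes the test conservative, if it has any effect.

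The evidence that baseline Kmax is prognostic is also indirect, and this too stands. The table has no correlation, regression or baseline SD. Its rows appear to be successive follow-up of overlapping eyes from one preliminary, uncontrolled series, so they are not seven confirmations, and the 6- and 7-year rows rest on five and four eyes with gaps of about 0.06 and 0.11 percentage points. A few extreme eyes could produce the 6-month gap. For illustration, 191 eyes with SD 2.7 D and no relation to baseline, plus five eyes at 80 D that flatten by 28 D, give a mean change near −1.25 D, an SD of 5.1 D and a gap of 0.40 points, against 0.48 in the table. Regression to the mean may contribute as well, although adjustment gains precision from a baseline–change correlation whatever its cause. No document gives outcomes by randomisation class.

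A second tempting inference is that 2.7 D is too small and the trial underpowered, since the same paired-t reading implies 5.24 D at 6 months and 3.86 D at 1 year. The documents do not support that conclusion. The test is unnamed, extreme eyes may inflate the figure, and under the same reading the protocol's 23-eye series implies about 2.5 D (2.01 × √23/3.79). The evidence is mixed.

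What the objection does not remove is the gain itself: the covariates are already collected, and using them costs almost nothing even if they prove uninformative.

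**Conclusion.** This is a worthwhile improvement, not the correction of a mistake. The planned unadjusted test is valid and its power statement reproduces, but it forgoes precision. If baseline Kmax explains 10% or 20% of the variance, adjustment adds 4.8 or 9.1 percentage points of power at SD 2.7 D, and 6.3 or 12.4 points at SD 3.0 D. These figures rest on 459 completers, 1:1 allocation, a true difference of zero and an assumed R². The K-max table makes such an R² plausible but does not establish it. Adjustment is not a safeguard against a much larger SD: at 3.5 D power stays below 80% with either R².

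As an optional note only: 2.7 D has no stated source, and completer power at 510 enrolled falls below 80% once the SD exceeds 2.74 D. That limit is not general. It is 2.89 D if all 510 count with the same SD, as in the intent-to-treat analysis, and 2.97 D for the protocol's enrolment of 600 less 10%. The documents do not show 2.7 D to be wrong.

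**What to change.** Replace the test sentence in SAP, Null and Research Hypotheses, with wording such as:

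> The primary analysis is a linear model of change in Kmax from baseline to 6 months on treatment, baseline Kmax and the classification as recorded at randomisation, with sparse classes pooled by a rule set in advance. Equivalence is concluded if the 90% CI of the adjusted difference lies within ±0.75 D, in both the per-protocol and intent-to-treat populations. The unadjusted two one-sided test is a sensitivity analysis.

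The class should be taken as recorded because the severity definitions in Protocol, Randomization, leave flat keratometry from 51.00 D to below 51.25 D unassigned, and allow an eye below 51.00 D with astigmatism of at least 8 D to be both mild and moderate.

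The change must be made before the treatment comparison is analysed; that is the workable deadline, since neither document describes masking in this trial. If the comparison has already been analysed, report the model as supportive only.

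The cost is one model statement and a pooling rule, with no new data. Optionally, add the source of 2.7 D and one line of unadjusted completer power: 88% at SD 2.5 D, 82% at 2.7 D, 70% at 3.0 D, 48% at 3.5 D and 28% at 4.0 D.

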### *Secondary Efficacy Outcomes*

The secondary efficacy outcome measures are the changes from baseline to 6 months after treatment in corrected distance visual acuity, uncorrected distance visual acuity, and minimum corneal thickness assessed by corneal tomography. The visual acuities will be measured with Snellen charts and converted to the logarithm of the minimum angle of resolution (logMAR) for statistical analysis. A 2-sided, 2-sample t test will be run for the per-protocol population at a 0.05 significance level.

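### Secondary outcomes get only an unadjusted per-protocol t test, with no randomised-population estimate, no baseline adjustment and no stated interval

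*SAP*

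**What the plan says.** The SAP frames the trial as an equivalence comparison. Its section on hypotheses makes non-equivalence of the two regimens the null, and says that "the research hypothesis is that they do produce equivalent results". For Kmax it specifies the matching test, "Equivalence will be assessed with a 2 one-sided test at the 0.05 significance level", with a margin of ±0.75 D. On populations it says (Main Outcome Measure): "This will be assessed for the per-protocol population as well as the intent-to-treat (randomized) population".

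The section on Secondary Efficacy Outcomes covers 6-month changes in "corrected distance visual acuity, uncorrected distance visual acuity, and minimum corneal thickness assessed by corneal tomography". Its only analysis statement is "A 2-sided, 2-sample t test will be run for the per-protocol population at a 0.05 significance level". It gives no covariates, margin, SD, confidence interval, randomised-population analysis or rule for interpreting the result.

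The Protocol's Data Analysis section adds a general two-sided 0.05 rule. Its Randomization section blocks on diagnosis, with keratoconus split into mild, moderate and severe. The SAP's Exploratory Analysis does plan confidence intervals for the fellow-eye comparison, so an exploratory analysis has a stated interval and the secondary outcomes do not.

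**The concern.** Acuity and corneal thickness are what a reader would look at next when judging whether the two dosing intervals are interchangeable. For these outcomes the plan drops three things.

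- **Randomised-population check.** Exclusions from the per-protocol set happen after randomisation and can differ between arms. For Kmax the second population would expose this. For the secondary outcomes nothing would.
- **Adjustment.** The baseline value of each outcome and the randomisation class are already collected, and the two-sample t test uses neither.
- **Interval.** The null hypothesis of the t test is no difference, the reverse of the SAP's own null of non-equivalence. Failing to reject it says nothing about how large a difference remains plausible. Without an interval, a p-value above 0.05 could be misread as similarity.

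**Working it through.** **Inputs.** From the SAP (Null and Research Hypotheses): 510 patients, 10% loss, SD 2.7 D, margin ±0.75 D, no true difference, each one-sided test at 0.05, 80% power. Assumed: 1:1 allocation, which the documents do not state. The documents give no SD, margin or per-protocol set size for the secondary outcomes, so the secondary results are in SD units.

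**The plan's own figure.** With no true difference, 80% power for two one-sided tests needs 90% for each. Per arm:

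n = 2 × 2.7² × (1.645 + 1.282)² / 0.75² ≈ 222

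This gives 444 in total, and 444 / 0.9 = 494 after allowing for loss. Using the t distribution gives 223 per arm, 446 in total and 496 enrolled. At 510 less 10%, power is 81.5% to 81.7%. The statement "Enrollment of 510 patients will provide 80% power to determine whether the 2 treatment arms are equivalent within this margin of equivalence" is therefore reproduced closely enough, and it concerns Kmax only.

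**The secondary t test.**
1. Evaluable per arm: 510 × 0.9 / 2 = 229.5. This is expected completers, so under the SAP's enrolment it is an upper bound for the per-protocol set.
2. Standard error of a difference: √(2 / 229.5) = 0.0934 SD.
3. Difference detectable with 80% power: (1.96 + 0.842) × 0.0934 = 0.26 SD.
4. Kmax margin in SD units: 0.75 / 2.7 = 0.278.
5. Probability of a non-significant result at true difference d: Φ(1.96 − d / SE).
   - d = 0.20: Φ(1.96 − 2.14) = 43%
   - d = 0.278: Φ(1.96 − 2.98) = 15%

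**Range.** The same formula for other set sizes:

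| Evaluable per arm | Basis | SE (SD units) | Non-significant at 0.20 SD | Non-significant at 0.278 SD |
|---|---|---|---|---|
| 200 | assumed smaller per-protocol set | 0.100 | 48% | 21% |
| 229.5 | SAP, 510 less 10% | 0.0934 | 43% | 15% |
| 270 | Protocol, 600 less 10% | 0.0861 | 36% | 10% |

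**Comparison.** Two one-sided tests with the margin at 0.278 SD would wrongly declare equivalence about 5% of the time when the true difference sits at that margin. Taking p above 0.05 as similarity would do so about 15% of the time.

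**What an interval would show.** The unadjusted 95% half-width is 1.96 × 0.0934 = 0.18 SD. Adjusting for baseline multiplies it by roughly √(1 − r²), where r is the correlation of the change with its baseline value. The documents do not give r, so the gain in precision cannot be sized here.

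**The case against.** A reader might infer that the plan commits to treating a non-significant secondary result as support for equivalence. The documents do not support that. The margin, SD and power statement apply to Kmax, and no section says how a null secondary result will be described. The most that can be said is that such a result could be misread.

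A reader might also infer that the secondary results would be worthless for either purpose. That also goes too far. A difference test beside one powered equivalence claim is a coherent choice. It follows the Protocol's two-sided rule and its stated aim (Rationale) of looking for dosing effects. Per-protocol analysis is not wrong in itself in an equivalence trial; the weakness is using it alone. Treatment is a single session, so many departures may simply be missed 6-month visits, and the documents give no basis for the size or direction of any bias. A two-sample comparison also has a corresponding 95% interval, and the SAP does not rule out reporting it.

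The figures can be challenged too. A difference of 0.20 SD lies inside the only yardstick in the documents: on the Kmax scale it is 0.20 × 2.7 = 0.54 D, below 0.75 D. That is why the 0.278 SD figure belongs beside it. Applying the Kmax yardstick to acuity or thickness is itself an assumption.

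Finally, adding a randomised-population analysis raises the question of missing data. The SAP's only rule is last observation carried forward, stated for the main outcome. Extended to uncorrected acuity, it could carry forward Day 1 or Week 1 values, taken soon after epithelial removal. For corrected acuity and tomographic thickness nothing is scheduled between screening and Month 3, so an early dropout would be given a change of zero. The fix has to deal with this.

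These objections lower the severity. They do not supply the missing randomised-population estimate, the adjustment or the stated interval.

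**Conclusion.** The point holds as an analysis gap of low severity. The secondary outcomes are planned in the per-protocol set only, without adjustment and without a stated interval, although the trial's hypothesis is equivalence and its primary outcome is analysed in both populations. If non-significance were taken as similarity, the error would be about 15% at 0.278 SD with 229.5 per arm (10% to 21% over 270 to 200 per arm), against the 5% accepted for Kmax. At 0.20 SD non-significance occurs about 43% of the time (36% to 48%).

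These figures rest on 1:1 allocation, a normal approximation, assumed set sizes and the SD scale. What they mean in logMAR or microns cannot be stated from the documents. The Kmax analysis and its conclusion are unaffected.

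**What to change.** Replace the analysis sentence under Secondary Efficacy Outcomes with a short paragraph that says:

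- For each secondary outcome, the between-arm difference in 6-month change will be estimated with adjustment for that outcome's baseline value and the randomisation class, and reported with a 95% confidence interval.
- This will be done in both the randomised and the per-protocol populations.
- For the randomised population, missing values will be handled by a method that does not carry forward Day 1 or Week 1 uncorrected acuity, such as a repeated-measures model on the observed Month 3 and Month 6 values. The paragraph should state the missing-at-random assumption behind such a model. Patients seen at neither visit contribute no post-treatment value to it.
- Conclusions will be drawn from the interval, and a non-significant p-value will not be described as equivalence.

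No secondary margins need to be set for this. The cost is one SAP paragraph and a few extra model runs on data already scheduled for collection.

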### *Safety Analysis*

The safety analysis will tabulate adverse events for all treated eyes (both study eyes and fellow eyes).

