ready mode) powers the device; the Start/Stop button controls UVA emission; and, status display lights (Red- Internal error, yellow-UV emission, Green-Device is powered, but no UV emission) indicate the status of the UV-X™ device. A battery operated ***UV Light detector***, with a built-in low battery warning, is used to check the UV light irradiation in the treatment plane before patient treatment. The UV Light detector consists of a ***Sensor Probe and an indicator***. The ***Sensor Probe Adapter*** with a Sensor Probe is permanently mounted to the UV-light illumination system to shield the beam aperture and should only be removed for treatment.

Riboflavin Ophthalmic Solution

The riboflavin ophthalmic solution is covered under IND (redacted).

Objectives

The primary objective of this study is to evaluate two riboflavin-dosing regimens for corneal collagen cross-linking to slow the progressive changes in corneal curvature in eyes with progressive keratoconus or post refractive ectasia.

Efficacy and Safety

The primary efficacy outcome measure is change in corneal curvature, as measured by maximum keratometry (Kmax). Secondary efficacy measurements will include: pachymetry, corrected distance acuity (CDA), and manifest refraction. Safety assessments will mean reporting any adverse events. All subjects will be evaluated at baseline, Day 1, Week 1 and 3 and 6 months after treatment with vision and intraocular pressure assessed at each visit.

Ophthalmic medical records after subjects exit the study will be retrospectively reviewed to assess visual changes and incidence of any subsequent ocular interventions.

Patient Population

Six hundred patients will be enrolled in the study.

Inclusion Criteria:

Subjects who have one or both eyes that meet all of the following criteria will be considered candidates for this treatment:

1. 10 years of age or older
2. Having documented ectasia on topography or tomography after previous refractive surgery OR documented keratoconus on topography or tomography. Subjects > 32 years old who have not had prior refractive surgery must have a diagnosis of progressive keratoconus defined as one or more of the following changes over a period of 36 months or less before randomization:

- a. An increase of ≥ 1.00 D in the steepest keratometry value (or sim K)
 - b. An increase of ≥ 1.00 D in regular astigmatism evaluated by subjective manifest refraction

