Follow-Up Visits (1 Day, 1 Week, 3 and 6 months)

A treatment flow chart summarizing the follow-up examination schedule and required procedures to be performed at each treatment visit is provided in Appendix A. All subjects will be seen at 1 day, 1 week, 3, and 6 months. If a study participant is unable to return to the study site for the 1-week exam, they may see a local doctor and efforts will be made to obtain copies of this exam.

The following will be performed at each visit unless noted otherwise.

- UCVA distance
- BSCVA distance (omit on Day 1 and Week 1)
- Manifest refraction (omit on Day 1 and Week 1)
- Pentacam measurements (omit on Day 1 and Week 1) , including
 - Pachymetry
 - Scheimpflug photography
- Corneal topography (omit on Day 1 and Week 1)
- Intraocular pressure (by Goldmann applanation tonometry (omit on Day 1)
- Slit lamp examination of the cornea, anterior chamber and lens
- Optical coherence tomography (OCT, omit on Day 1)

Reasonable effort will be made by telephone and mail to contact subjects who miss a scheduled follow-up visit.

Retreatment

Any subject who is at least 1-year post- cross-linking treatment and who shows signs of progression at two visits will be considered for retreatment. Retreated eyes will not be included in the efficacy analysis and will be dosed at 5 minute intervals during irradiation.

Fellow Eyes

Patients who, at the discretion of the investigator, could benefit from the study treatment in both eyes may have both eyes treated; however, only the first treated eye per patient will be considered for the efficacy analysis. All treated eyes will be included in the safety analysis. Fellow eyes can be treated on the same or a different day as the randomized eye; this decision will be made by the patient and the principal investigator.

Safety Monitoring

During the CXL treatment procedure, subjects will be observed closely to detect the occurrence of any adverse events or complications. On the day of treatment and at each follow-up visit, the subjects will be questioned to determine whether any adverse events might have occurred since the last examination. The presence or absence of adverse events or complications will be documented.

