Ophthalmic safety will be evaluated by slit lamp examination of the operated eye, measurements of refraction, and measurement of visual acuity. In the case of an adverse event or complication, the frequency of the examinations will be increased until the problem is resolved. Any complications or visual adverse events will be recorded in the medical record and reported to the FDA.

UV-X and Riboflavin Accountability

All use of the UV-X™ Illumination System and Riboflavin Ophthalmic Solution will be under the direct supervision of the designated study coordinator. The use of the Riboflavin solution will be maintained in a clinical treatment program log.

Data Analysis

Statistical analyses will be performed using SAS[®] software. All enrolled subjects will be included in the safety analysis. Testing will be 2-sided and P-values < 0.05 will be considered significant. To preclude confounding effects between fellow eyes, only the first treated eye per subject will be included in the efficacy analysis.

Ethical and Regulatory Considerations

This treatment will be conducted in accordance with FDA's Good Clinical Practice regulations.

Informed Consent

In accordance with the provision of 21 CFR Part 50, each subject will provide written informed consent for participation in this treatment prior to the use of the investigational device. The treatment will be explained to the patients, or guardian, by the surgeon. The alternatives to this treatment will be discussed together with the potential hazards of the proposed treatment. The potential patients will be informed that they are free to not treat their condition or to obtain treatment outside the United States. We will emphasize the fact that this treatment has not been approved by the FDA, and just because their disease has progressed in the past does not mean that it will continue to progress.

Institutional Review Board

This proposal and the informed consent form will be approved initially and reviewed annually by the Institutional Review Board.

Adverse Events

For all adverse events, a description of the event, date first observed, action taken, and its resolution will be reported.

Non-serious or Anticipated Drug or Device Adverse Events

Non-serious or anticipated drug or device adverse events and complications will be documented on the case report forms and tabulated for reporting in the annual reports to FDA.

Serious and Unanticipated Adverse Device Effects

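### The planned safety analysis is an adverse event table only, so a loss of corrected acuity or a pressure rise not classed as an adverse event appears in no planned table

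*SAP*

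**What the plan says.** The protocol describes safety in two ways. Under Efficacy and Safety: "Safety assessments will mean reporting any adverse events". Under Safety Monitoring: "Ophthalmic safety will be evaluated by slit lamp examination of the operated eye, measurements of refraction, and measurement of visual acuity". IOP is not in that second list. It appears under Efficacy and Safety as a scheduled measurement, "with vision and intraocular pressure assessed at each visit".

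The SAP's Safety Analysis section is one sentence: "The safety analysis will tabulate adverse events for all treated eyes (both study eyes and fellow eyes").

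Acuity enters the SAP only under Secondary Efficacy Outcomes, which cover change to 6 months in "corrected distance visual acuity, uncorrected distance visual acuity, and minimum corneal thickness assessed by corneal tomography". The analysis is a comparison of means: "A 2-sided, 2-sample t test will be run for the per-protocol population at a 0.05 significance level". The protocol's Data Analysis section adds that "only the first treated eye per subject will be included in the efficacy analysis". The SAP's Exploratory Analysis does use fellow eyes, but only for the main outcome, maximum keratometry.

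Protocol Table 1 schedules corrected acuity at screening, Month 3 and Month 6, and IOP at screening, Week 1, Month 3 and Month 6.

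**The concern.** The SAP carries none of the three Safety Monitoring measures into a safety summary. A difference in mean acuity says little about a few eyes that lose several lines while most hold steady or gain, and those few eyes are what a safety reader looks for. Per-protocol study eyes at least have that mean. Study eyes outside the per-protocol set, and all fellow eyes, have no acuity analysis, although the safety population is all treated eyes. IOP is measured and then not used.

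What remains is classification as an adverse event. Neither document says how large an acuity loss or pressure rise must be to count as one, and neither describes masking of the person who decides.

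The trial aims to show that two dosing intervals are equivalent on maximum keratometry, and its Rationale says the effect of dosing regimen on both efficacy and safety has not been studied. A report of equivalence with no adverse event imbalance and similar mean acuity could coexist with a minority of eyes that lost vision.

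**Working it through.** **Where each measurement ends up**

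| Measurement | Named in Safety Monitoring | Collected | Planned analysis |
|---|---|---|---|
| Corrected acuity | Yes, as visual acuity | Screening, Months 3 and 6 | Mean change to 6 months, per-protocol study eyes |
| Refraction | Yes | Screening, Months 3 and 6 | None in the SAP |
| Slit lamp | Yes | Screening and every follow-up visit | None, unless a finding is an adverse event |
| IOP | No | Screening, Week 1, Months 3 and 6 (Table 1) | None |

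So the gap covers changes that are not classed as adverse events.

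**Plan's own figure.** The documents give no number for safety. The SAP's 510 patients relate to the keratometry equivalence test, and I use that figure only to set the number of eyes per arm. It reproduces adequately. With 1:1 allocation (assumed) and a true difference of zero, n = 2 × 2.7² × (1.645 + 1.282)² / 0.75² = 222 per arm, and 222 / 0.9 gives 247 per arm, 494 in total. With 510 × 0.9 = 459 evaluable, power is about 82% against the stated 80%.

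**Illustration: eyes per arm.** 459 / 2 = 229.5, taken as 230.

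**Assumed, because the documents give neither an acuity SD nor a loss rate:** SD of change in corrected acuity 0.15 to 0.25 logMAR; one arm has 3 percentage points more eyes that lose 0.3 logMAR.

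**Planned t test.** Mean difference = 0.03 × 0.3 = 0.009 logMAR. Standard error = SD × √(2/230). Two-sided power at 0.05:

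| SD (logMAR) | Standard error | Difference / SE | Power |
|---|---|---|---|
| 0.15 | 0.0140 | 0.64 | 9.8% |
| 0.20 | 0.0187 | 0.48 | 7.7% |
| 0.25 | 0.0233 | 0.39 | 6.7% |

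These are close to the test's own 5% error rate.

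**Counting eyes.** Two-sided Fisher exact test at 0.05, with power summed over two binomials of 230. The p-value is for the counts nearest expectation:

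| True loss rates | Power | Counts | p |
|---|---|---|---|
| 3% vs 0% | 69% | 7 vs 0 | 0.015 |
| 4% vs 1% | 43% | 9 vs 2 | 0.06 |
| 5% vs 2% | 32% | 12 vs 5 | 0.14 |
| 6% vs 3% | 27% | 14 vs 7 | 0.18 |

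The excess is 3 points in every row, so the assumed mean difference and t-test power stay roughly as above. Counting is better in each row, but its advantage depends heavily on the background rate.

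**Day 1 IOP.** Efficacy and Safety includes Day 1 in the follow-up schedule and has IOP taken at every visit. The Follow-Up Visits list reads "Intraocular pressure (by Goldmann applanation tonometry (omit on Day 1"), and Table 1 has no Day 1 entry for IOP.

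**The case against.** The strongest reply is that the SAP does what the protocol asks. Efficacy and Safety equates safety assessment with adverse event reporting, and the SAP tabulates adverse events for every treated eye, fellow eyes included. On that view the Safety Monitoring sentence describes how events are detected and promises no table. Subjects are asked about events at each visit, the presence or absence of events is documented, and visual adverse events are recorded and reported to the FDA.

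Much of this stands. A reader might infer that the SAP contradicts the protocol. The documents do not support that: the tension is between two protocol sections, and the SAP follows one of them. A reader might also infer that the protocol makes IOP a criterion of ophthalmic safety; it is a scheduled measurement only. Nor does the prednisolone prescription add much. It runs for two weeks, whereas the protocol's Background warns about long-term topical steroid use.

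It is also fair to say that 3% vs 0% flatters counting. A zero background rate is favourable in eyes treated for progressive disease, and setting a p-value of 0.015 against a power of 7-10% would compare different quantities.

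What the reply does not remove is the missing threshold, the absence of any acuity summary for fellow eyes and study eyes outside the per-protocol set, and the absence of any IOP summary.

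**Conclusion.** The point holds in limited form. The safety analysis is an adverse event tabulation, acuity is analysed only as a mean in per-protocol study eyes, and IOP is not summarised. A vision loss or pressure rise not classed as an adverse event therefore appears in no planned table. It would be too strong to say that such changes go uncounted altogether, because any that are classed as adverse events are counted.

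On size, the mean comparison is nearly blind to a 3-point excess of eyes losing 0.3 logMAR (about 7-10% power). Counting does better, at about 69% with no background loss and 27-43% with a 1-3% background. These figures rest on an assumed SD, loss rate and 1:1 allocation. They support showing the counts with confidence intervals; they do not show that a Fisher test would reliably find a difference. The primary keratometry analysis is unaffected, so this is a change that should be made rather than one on which the trial's main conclusion depends.

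**What to change.** Add to the SAP's Safety Analysis section, from data already collected:

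- **Acuity.** The number and percentage of eyes losing corrected distance acuity from their own baseline at Month 3 and Month 6, by amounts fixed before analysis, with confidence intervals. At least 0.2 and at least 0.3 logMAR would serve as examples; the documents give no cut-offs, so the sponsor should set them.
- **IOP.** A descriptive summary of change from baseline at each visit where it is measured.

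Present study eyes by randomised arm over all treated study eyes with data, not only the per-protocol set. Present fellow eyes separately; all are assigned 5-minute dosing, so they offer no randomised comparison. Report both tables beside the adverse event table, and do not move eyes into that table automatically, since this would change what counts as an adverse event and could label disease progression as treatment harm.

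In the protocol, state whether the Safety Monitoring measures are means of detecting events or outcomes to be summarised, so that this section and Efficacy and Safety agree. Reconcile Efficacy and Safety with Follow-Up Visits and Table 1 on Day 1 IOP.

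The cost is two extra tables and some SAP wording, with no new visits or measurements. Some counted losses may reflect the underlying disease, and the table notes should say so.
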